## 6.2.4.6. Neurological Adverse Events

Neurological AEs have been observed uncommonly following treatment with anti-PD-1 therapies. Neurological AEs may manifest as central abnormalities (eg, aseptic meningitis or encephalitis) or peripheral sensory/motor neuropathies (eg, Guillain-Barre Syndrome). The onset has been observed as early as after a single treatment. Early recognition and treatment of neurologic AEs is critical to their management (see Table 14). Subjects should be advised to seek medical evaluation if they notice impairment in motor function (eg, weakness), changes in sensation (eg, numbness), or symptoms suggestive of possible central nervous system abnormalities such as new headache or mental status changes.

Guidelines for dose delay can be found in Section 6.2.2.		
Grade 1	Monitor per protocol	
	Worsening: treat as $\geq$ Grade 2	
	Immediately: treat symptoms according to institutional standards; consider 0.5-1.0 mg/kg/d	
Grade 2	methylprednisolone IV or oral equivalent	
	Worsening: treat as Grade 3-4	
	Immediately: consult neurologist; treat symptoms according to institutional standards; start	
	1.0-2.0 mg/kg/d methylprednisolone IV or IV equivalent; prophylactic antibiotics	
Grade 3-4	Worsening or atypical presentation: consider immunoglobulins IV (IVIG) or other	
	immunosuppressive therapies according to institutional standards	
	Improvement to ≤Grade 2: taper steroids over at least 4 weeks	
General	Patients on IV steroids may be switched to an equivalent dose of oral corticosteroids	
	(eg, prednisone) at start of tapering or earlier, once sustained clinical improvement is observed.	
	The lower bioavailability of oral corticosteroids need to be considered	

 Table 14:
 Management of Neurological Adverse Events

## 6.2.4.7. Pulmonary Adverse Events

Pulmonary AEs including radiographic changes (eg, focal ground glass opacities and patchy infiltrates) indicative of drug-related pneumonitis have been observed in subjects receiving anti-PD-1 therapies. These pulmonary AEs were either asymptomatic or associated with symptoms such as dyspnea, cough, or fever. The initial occurrence of pulmonary AEs may be as early as after a single dose of anti-PD-1 therapies or delayed after prolonged therapy. Early recognition and treatment of pneumonitis is critical to its management (see Table 15). Subjects should be advised to seek medical evaluation promptly if they develop new-onset dyspnea, cough, or fever or if they have worsening of these baseline symptoms.

Guidelines for dose delay can be found in Section 6.2.2.		
	Monitor for symptoms every 2-3 days; consider pulmonary and infectious-disease consult;	
Grade 1	re-image every 3 weeks	
	Worsening: treat as ≥Grade 2	
	Monitor symptoms daily; re-image every 1-3 days; pulmonary and infectious-disease consultation;	
	consider bronchoscopy and lung biopsy; consider hospitalization	
Grade 2	Immediately: start 1.0 mg/kg/d methylprednisolone IV or oral equivalent; prophylactic antibiotics	
	Persistence for 2 weeks or worsening: treat as Grade 3-4	
	Improvement to ≤Grade 1 or baseline: taper steroids over at least 4 weeks	
	Hospitalize; pulmonary and infectious-disease consult; consider bronchoscopy and lung biopsy	
	Immediately: 2-4 mg/kg/d methylprednisolone or IV equivalent; add prophylactic antibiotics;	
Grade 3-4	Persistence for 2 days or worsening: add immunosuppression (eg, infliximab, cyclophosphamide,	
	IVIG, or mycophenolate mofetil)	
	Improvement to $\leq$ Grade 2: taper steroids over at least 6 weeks	
	Patients on IV steroids may be switched to an equivalent dose of oral corticosteroids	
General	(eg, prednisone) at start of tapering or earlier, once sustained clinical improvement is observed.	
	The lower bioavailability of oral corticosteroids need to be considered	

Table 15:Management of Pulmonary Adverse Events

#### 6.2.4.8. Uveitis and Visual Complaints

Immune therapies have been uncommonly associated with visual complaints. Inflammation of components within the eye (eg, uveitis) is an uncommon, but clinically important, event. An ophthalmologist should evaluate visual complaints with examination of the conjunctiva, anterior and posterior chambers, and retina (see Table 16). If the subject has double vision, prompt medical evaluation should occur. In addition to ocular inflammatory events, a work-up should also consider pituitary inflammation as a cause.

 Table 16:
 Management of Uveitis and Visual Complaints

Guidelines for dose delay can be found in Section 6.2.2.	
Grade 1	Thorough eye examination
Grade 2	Topical corticosteroids should be considered
	Persisting despite topical steroids, treat as Grade 3-4
Grade 3-4	Thorough eye examination
	Systemic corticosteroids

## 6.2.4.9. Lipase/Amylase Elevations

Asymptomatic elevations in lipase and amylase have been reported in anti-PD-1 therapy studies in which systemic monitoring was used. Very few subjects reported associated symptoms (eg, abdominal pain) or radiographic findings (eg, stranding) consistent with pancreatitis. Thus, there does not seem to be clinical significance to the elevated laboratory values. The recommended management of anti-PD-1 therapy-related elevated lipase/amylase values centers around close observation. Physicians should ensure that subjects have no associated symptoms consistent with pancreatitis, such as abdominal pain. Corticosteroids do not seem to alter the natural history of lipase/amylase elevations. Laboratory values tend to fluctuate on a day-to-day basis and eventually return to baseline or low-grade levels over the course of weeks, whether or not subjects receive corticosteroids. Asymptomatic elevations should be monitored approximately weekly.

## 6.2.5. Infection

Subjects with a documented infectious complication should receive oral or IV antibiotics or other anti-infective agents as considered appropriate by the treating investigator for a given infectious condition, according to standard institutional practice.

## 6.3. Treatment of Infusion-related Reactions (IRRs)

## 6.3.1. Guidelines for Management of Daratumumab IRRs

For infusion reactions of any grade/severity, immediately interrupt the daratumumab infusion and manage symptoms. Management of infusion reactions may require reduction in the rate of infusion, or discontinuation of daratumumab (see Table 17).

Guidelines for dose delay can be found in Section 6.1.5.		
Severity of IRR	Management	
Grade 1-2 (mild to moderate)	Once IRR symptoms resolve and the subject's condition is stable, the infusion may be restarted at the investigator's discretion. Resume the infusion at no more than half the rate at which the IRR occurred. If the subject does not experience any further IRR symptoms, infusion rate escalation may resume at increments and intervals as clinically appropriate up to the maximum rate of 200 mL/hr (see Table 5).	
Grade 2 or higher laryngeal edema, or bronchospasm	If the subject experiences a Grade 2 or higher event of laryngeal edema, or a Grade 2 or higher event of bronchospasm that does not respond to systemic therapy and does not resolve within 6 hours from onset, then the subject must permanently discontinue daratumumab treatment.	
Grade 3 (severe)	Once reaction symptoms resolve, consider restarting the infusion at no more than half the rate at which the IRR occurred. If the subject does not experience additional symptoms, then resume infusion rate escalation at increments and intervals as outlined in Table 5. Repeat the procedure above in the event of recurrence of Grade 3 symptoms or discontinue the subject from treatment. At the subsequent infusion, permanently discontinue daratumumab if the subject experiences a Grade 3 IRR for a third time.	
Grade 4 (life threatening)	Permanently discontinue daratumumab treatment.	

 Table 17:
 Management Guidelines for Daratumumab Infusion-related Reactions

IRR=infusion-related reaction.

## 6.3.2. Guidelines for Management of JNJ-63723283 IRRs

For infusion reactions of any grade/severity, immediately interrupt the JNJ-63723283 infusion and manage symptoms. Management of infusion reactions may require reduction in the rate of infusion, or discontinuation of JNJ-63723283 (see Table 18).

Guidelines for dose delay can be found in Section 6.2.2.		
Severity of IRR	Management	
Grade 1	No intervention indicated; remain at bedside and monitor subject until recovery from symptoms, Consider diphenhydramine 50 mg (or equivalent) and or paracetamol 325 to 1000 mg (acetaminophen) at least 30 minutes before additional study drug administration	
	Stop infusion; start IV saline infusion; give diphenhydramine 50 mg (or equivalent) IV and/or paracetamol 325 to 1000 mg (acetaminophen); consider corticosteroids and bronchodilator therapy; remain at bedside and monitor subject until recovery from symptoms	
Grade 2	Restart infusion at 50% of initial rate: if no further complications ensue after 30 minutes, the rate may be increased to 100% of the original infusion rate; monitor subject closely.	
	Symptoms recur: stop and discontinue further treatment at that visit; administer diphenhydramine 50 mg IV, and remain at bedside and monitor the subject until resolution of symptoms. The amount of study drug infused must be recorded on the CRF.	
	Stop infusion; start IV saline infusion; recommend bronchodilators, epinephrine 0.2 to 1 mg of a 1:1,000 solution for subcutaneous administration or 0.1 to 0.25 mg of a 1:10,000 solution injected slowly for IV administration, and/or diphenhydramine 50 mg IV with methylprednisolone 100 mg IV (or equivalent), as needed.	
Grade 3-4	Subject should be monitored until the investigator is comfortable that the symptoms will not recur. Study drug will be permanently discontinued. Investigators should follow their institutional guidelines for the treatment of anaphylaxis. Remain at bedside and monitor subject until recovery from symptoms. In the case of late-occurring hypersensitivity symptoms (eg, appearance of a localized or generalized pruritis within 1 week after treatment), symptomatic treatment may be given (eg, oral antihistamine, or corticosteroids).	
General	Prophylactic medications (after initial event): diphenhydramine 50 mg (or equivalent) and/or paracetamol 325 to 1000 mg (acetaminophen) at least 30 minutes before additional study drug administrations; if necessary, corticosteroids (recommended dose: up to 80 mg of IV methylprednisolone or equivalent) may be used	
	Appropriate resuscitation equipment should be available in the room and a physician readily available during the infusion of study drug.	

 Table 18:
 Management of Infusion-Related Reactions for JNJ-63723283

## 6.4. Dosage and Administration for Daratumumab Monotherapy Period

The start of each cycle (i.e., Day 1) may occur within  $\pm 3$  days of the scheduled day in order to accommodate the schedule of the site or subject. If the start of a cycle is delayed, Day 1 of the subsequent cycle should be adjusted accordingly to maintain the 28-day cycle duration. The weekly or bi-weekly study treatment administrations (i.e., Day 8, 15, and 22 dosing dates) may occur within  $\pm 1$  day of the scheduled day to accommodate the schedule of the site or subject. Changes to within-cycle dosing should not impact Day 1 of the next cycle.

## 6.4.1. Daratumumab Monotherapy

Daratumumab will be administered to subjects as described in the Time and Events Schedule Table 24. Subjects will continue to receive daratumumab until disease progression, unacceptable toxicity, or other reasons as listed in Section 10. Refer to the Investigational Product Preparation Instructions (IPPI) and the Site Investigational Product and Procedures Manual (SIPPM) for detailed descriptions for preparation and administration of daratumumab.

## 6.4.1.1. Daratumumab Treatment Schedule and Administration

Each cycle is 28 days. The daratumumab administration dose and schedule is summarized below:

• Daratumumab 16 mg/kg IV will be administered once every week (Weeks 1 to 8); then once every other week for 16 weeks (Weeks 9 to 24); thereafter once every 4 weeks (Week 25 onwards).

Each subject's dose will be calculated based on the subject's weight at Cycle 1 Day 1 rounded to the nearest kilogram. The dose of daratumumab does not need to be recalculated for weight changes <10% from baseline. Subjects will receive preinfusion medications and postinfusion medications as outlined in Sections 6.4.1.2 and 6.4.1.3.

The dilution volumes, initial infusion rates, and increment of infusion rates for the first, second, and subsequent doses in the absence of an infusion-related reaction >Grade 1 are provided in Table 19.

	Dilution Volume	Initial Infusion Rate (first hour)	Incremental Increases in Infusion Rate a	Maximum Infusion Rate
Week 1 infusion (Cycle 1 Day 1)	1000 mL	50 mL/hour	50 mL/every hour	200 mL/hour
Week 2 infusion b	500 mL	50 mL/hour	50 mL/hour every hour	200 mL/hour
Subsequent infusions c	500 mL	100 mL/hour	50 mL/hour every hour	200 mL/hour

Table 19: Daratumumab Administration

a. Consider titration of the infusion rate only in the absence of infusion-related reactions.

b. Dilution volume of 500 mL should be used only if there were no Grade 1 (mild) or greater infusion-related reactions during the first 3 hours of the first infusion. Otherwise, continue to use a dilution volume of 1000 mL.

c. Use a modified initial rate for subsequent infusions (ie, third infusion onwards) only if there were no Grade 1 (mild) or greater infusion-related reactions during a final infusion rate of ≥100 mL/h in the first two infusions. Otherwise, continue to use instructions for the second infusion.

Vital signs should be measured before the start of each daratumumab infusion and at the end of each daratumumab infusion. If a subject experiences any significant medical event, then the investigator should assess whether the subject should stay overnight for observation. If the subject has not experienced a significant medical event but is hospitalized overnight only for observation, then the hospitalization should not be reported as a serious adverse event.

## 6.4.1.2. Preinfusion Medication

In an effort to prevent infusion related reactions, all subjects will receive the following medications 1 to 3 hours prior to the start of each daratumumab infusion (see the Time and Events Schedule; Table 24):

- An antipyretic: paracetamol (acetaminophen) 650 to 1000 mg IV or orally (PO).
- An antihistamine: diphenhydramine 25 to 50 mg IV or PO, or equivalent). Avoid the use of IV promethazine (see Attachment 1 for a list of antihistamines that may be used).
- A corticosteroid: methylprednisolone 100 mg IV or PO or equivalent for the first 2 doses and 60 mg for all subsequent doses (after 2 consecutive daratumumab infusions are completed with no IRR adverse events). Substitutions for methylprednisolone are allowed (refer to Attachment 2).

In addition, a leukotriene inhibitor (optional; montelukast 10 mg PO) may be administered up to 24 hours before infusion as per investigator discretion.

If necessary, all PO preinfusion medications may be administered outside of the clinic on the day of the infusion, provided they are taken 1 to 3 hours before the infusion.

## 6.4.1.3. Postinfusion Medication

Postinfusion medication should be administered to reduce the risk of delayed infusion-related reactions in all subjects:

• Oral corticosteroid (20 mg methylprednisolone PO or equivalent in accordance with local standards) on the 2 days following each daratumumab administration (beginning the day after study drug administration). After 3 consecutive daratumumab infusions with no IRR adverse events, postinfusion corticosteroids should be administered per investigator discretion.

For subjects with a higher risk of respiratory complications (eg, subjects with COPD who have an FEV1 <80% or subjects with asthma), the following postinfusion medications should be considered:

- antihistamine (diphenhydramine or equivalent) on the first and second days after each infusion;
- short-acting  $\beta 2$  adrenergic receptor agonist such as salbutamol aerosol; and
- control medications for lung disease (eg, inhaled corticosteroids  $\pm$  long-acting  $\beta$ 2 adrenergic receptor agonists for subjects with asthma; long-acting bronchodilators such as tiotropium or salmeterol  $\pm$  inhaled corticosteroids for subjects with COPD).

In addition, these at-risk subjects may be hospitalized for monitoring for up to 2 nights after study drug administration. If these at-risk subjects are hospitalized, then their FEV1 should be measured and managed per local standards before discharge. If these subjects are not hospitalized, then a follow-up telephone call should be made to monitor their condition within 48 hours after each daratumumab administration. If the subject has not experienced a significant medical event but is hospitalized overnight only for observation, then the hospitalization should not be reported as a serious adverse event. Investigators may prescribe bronchodilators, antihistamines, and corticosteroids that are deemed necessary to provide adequate supportive care in the event a bronchospasm occurs after subjects are released from the hospital/clinic. If an at-risk subject experiences no major IRRs, then these postdose medications may be waived after 4 doses at the investigator's discretion.

## 6.4.1.4. Monitoring During and After Daratumumab Administration

Subjects should be observed carefully during study agent infusions. Trained study staff at the clinic should be prepared to intervene in case of any IRRs occurring, and resources necessary for resuscitation (eg, agents such as epinephrine and aerosolized bronchodilator, also medical equipment such as oxygen tanks, tracheostomy equipment, and a defibrillator) must be available at the bedside. If an IRR develops, then the infusion should be paused. Guidelines outlined in Section 6.3 must be followed to manage IRRs.

Subjects should be monitored for at least 2 hours after the completion of the first infusion and may be discharged if considered clinically stable and all other study procedures have been completed (see Table 20 below). The investigator will determine the duration of safety monitoring for subsequent administrations. In addition, subjects should be monitored for symptoms of tumor lysis syndrome, see Section 8.1.2.

Table 20:	Infusion Duration and Monitoring After Infusion of Daratumumab
-----------	--

Cycle 1 Day 1	Daratumumab – First infusion
	Daratumumab is administered over a 6 to 8 hour infusion period followed by a 2-hour
	observation period. The subject may be discharged if considered clinically stable and all
	other study procedures have been completed
Cycle 1 Day 8	Daratumumab – Second infusion
	If the first daratumumab infusion is well tolerated (defined as no Grade 1 or higher
	IRRs), then the second daratumumab infusion should administered over 3 to 4 hours,
	followed by a 2-hour observation period. However, if the first daratumumab infusion is
	not well tolerated, then the second daratumumab infusion will follow the C1D1
	daratumumab infusion schedule, as described above and in Table 5.
Cycle 1 Day 15	Daratumumab
	Daratumumab is administered over a 3 to 4 hour infusion period, followed by a 2-hour
	observation period.
Cycle 1 Day 22	Daratumumab
	Daratumumab is administered over a 3 to 4 hour infusion period, followed by a 2-hour
	observation period.
Cycle 2 Day 1 and	Daratumumab
subsequent infusions	If all the infusions in Cycle 1 are well tolerated, then starting on C2D1, the observation
-	period can be 1-hour after dosing of daratumumab. If not well tolerated (ie, Grade 1 or
	higher infusion-related reactions), then follow the C1D15 procedures.

## 6.4.1.5. Dose Delay

Dose modification of daratumumab is not permitted. Dose delay is the primary method for managing daratumumab-related toxicities.

On the first day of each new treatment cycle and before each daratumumab dose, the subject will be evaluated by the treating physician for possible toxicities that may have occurred after the previous dose(s). Toxicities are to be assessed according to NCI-CTCAE, Version 4.03. Dose delays will be made based on the toxicity experienced during the previous infusion or newly encountered on Day 1 of a new cycle.

The study treatment must be held if any of the following criteria below are met, to allow for recovery from toxicity, regardless of relationship to daratumumab.

The criteria for a dose delay are:

- Grade 4 hematologic toxicity, except for Grade 4 lymphopenia
- Grade 3 thrombocytopenia with bleeding
- Febrile neutropenia
- Neutropenia with infection, of any grade
- For all other adverse events, daratumumab should be withheld for Grade 3 or higher toxicities with the following exceptions:
  - Grade 3 nausea that responds to antiemetic treatment within 7 days
  - Grade 3 vomiting that responds to antiemetic treatment within 7 days
  - Grade 3 diarrhea that responds to antidiarrheal treatment within 7 days
  - Grade 3 fatigue that was present at baseline or that lasts for <7 days after the last administration of daratumumab
  - Grade 3 asthenia that was present at baseline or that lasts for <7 days after the last administration of daratumumab

Administration of daratumumab may be restarted upon recovery from toxicity to Grade 2 or baseline, with the exception of Grade 2 laryngeal edema, Grade 2 bronchospasm or febrile neutropenia, which must be fully recovered. If daratumumab administration does not commence within the prespecified window (Table 21) of the scheduled administration date, then the dose will be considered a missed dose. Administration may resume at the next planned dosing date. A missed dose will not be made up. Alternatively, dosing delays can be discussed with the Sponsor.

#### Table 21: Daratumumab-related Toxicity Management

Cycles	Frequency	Dose Held	Dosing Restart
1 and 2	Weekly (q1wk)	>3 days	Next planned weekly dosing date
3 to 6	Biweekly (q2wks)	>7 days	Next planned biweekly dosing date
7+	Every 4 weeks (q4wks)	>14 days	Next planned every 4 weeks dosing date

The start (ie, Day 1) of a cycle may be delayed up to 4 weeks. Day 1 of a cycle should never be skipped. If the start of a cycle is delayed, Day 1 of subsequent cycles should be adjusted accordingly to maintain the 28-day cycle duration. However, if a within-cycle dose (i.e., Day 8, Day 15, or Day 22) is delayed, then the dates of the subsequent within-cycle doses should **not** be adjusted.

If 2 consecutive planned doses of daratumumab are missed due to any adverse event, then consultation with the Sponsor is required before dosing may be continued.

For subjects whose dose is held for more than 28 days for any drug related adverse event or who miss 3 or more consecutive planned doses of daratumumab due to any adverse event, then the

treatment should be permanently discontinued. Dose holds of more than 28 days for other reasons should be discussed with the Sponsor.

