#### Attachment 11: Daratumumab Monotherapy Period For Subjects No Longer Receiving JNJ-63723283 In Combination With Daratumumab

#### **Overall Design for Daratumumab Monotherapy Period**

Each cycle is 28 days, and administration of daratumumab is to occur weekly for Cycles 1 and 2, every other week for Cycles 3 to 6, and every 4 weeks for Cycles 7 and onwards until disease progression, pregnancy, unacceptable toxicity, loss of follow-up, withdrawal of consent, or death. Scheduled assessments to be performed during the Daratumumab Monotherapy Period for Subjects No Longer Receiving JNJ-63723283 in Combination with Daratumumab are outlined in the Time and Events Schedule in Table 24.

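### In the Daratumumab Monotherapy Period, 6.4.1.5 gives two dosing dates for a Cycle 7+ dose when recovery comes 15 to 27 days late, and the missed-dose bullet of 10.1.1 is looser than 6.4.1.5 and inconsistent beyond Cycle 2

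*Protocol*

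**What the plan says.** **Schedule.** Attachment 11 of the protocol sets weekly dosing in Cycles 1 and 2, 2-weekly in Cycles 3 to 6, and "every 4 weeks for Cycles 7 and onwards until disease progression" or another listed stop. Table 24 shows Day 1 as the only dosing day from Cycle 7.

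**Late doses, first text.** Under 6.4.1.5, a dose not started within its Table 21 window counts as missed, and "A missed dose will not be made up". The Cycle 7+ row sets the window at 14 days. The restart is then the "Next planned every 4 weeks dosing date".

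**Late doses, second text.** The paragraph below Table 21 says: "The start (ie, Day 1) of a cycle may be delayed up to 4 weeks". It adds "Day 1 of a cycle should never be skipped" and shifts later cycles. Section 6.4 says the same about shifting: "Day 1 of the subsequent cycle should be adjusted accordingly to maintain the 28-day cycle duration". The paragraph then treats other doses separately ("if a within-cycle dose (i.e., Day 8, Day 15, or Day 22) is delayed") and leaves the dates of later within-cycle doses unchanged.

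**Permanent stop, 6.4.1.5.** Treatment should stop after a hold of more than 28 days for a drug-related adverse event, or for subjects who "miss 3 or more consecutive planned doses of daratumumab due to any adverse event". Holds of more than 28 days for other reasons go to the Sponsor for discussion.

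**Permanent stop, 10.1.1.** The missed-dose bullet requires a stop after more than three consecutive missed doses. It counts only daratumumab-related events and attaches a delay of up to 4 weeks in Cycles 1 to 6 and up to 6 weeks afterwards. Section 1.4 sends readers to 10.1.1 for the criteria that end monotherapy.

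**The concern.** From Cycle 7 every dose is a Day 1 dose. The Cycle 7+ row of Table 21 therefore applies only to doses that the next paragraph says are never skipped. Two sites with the same subject, recovered on the same day, can act differently and each be correct under one of the texts.

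The stop rules also differ in dose count, in which adverse events count, and in the length of delay. A reader who goes to 10.1.1, as Section 1.4 directs, finds a weaker missed-dose rule than the one in the dosing section.

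What is at stake is treatment conduct and safety for ongoing subjects. Monotherapy is the only treatment left in the study, and Cycle 7+ is its open-ended phase. These rules come into play when a subject has toxicity, and a permanent stop also ends study participation after the End of Treatment Visit (10.1.1).

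**Working it through.** The plan states no figure to reproduce, so the check is a comparison of the rules by day count. It assumes a continuous hold, a previous dose given on schedule and no Sponsor exception. It ignores the ±3-day scheduling allowance in 6.4.

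**1. Late dose in Cycle 7+.** The dosing interval is 28 days. Let L be the number of days late at which the subject is ready to be dosed.

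- Second text (give the dose): days since the last dose = 28 + L, for L up to 28.
- Table 21 (L above 14, dose missed): days since the last dose = 28 + 28 = 56.
- Difference = 56 − (28 + L) = 28 − L.

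| L (days late) | Interval if given | Interval if missed | Difference |
|---|---|---|---|
| 15 | 43 | 56 | 13 |
| 21 | 49 | 56 | 7 |
| 27 | 55 | 56 | 1 |
| 28 | 56 | 56 | 0 |

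The dosing dates differ for L from 15 to 27. At L = 28 only the label (missed or delayed) differs.

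**2. Internal consistency of the 10.1.1 bullet.** More than three missed doses means at least four. From the first to the fourth missed due date is 3 × interval; to the next due date is 4 × interval.

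| Cycles | Interval | 3 × interval | 4 × interval | Delay in 10.1.1 |
|---|---|---|---|---|
| 1–2 | 7 | 21 | 28 | 28 |
| 3–6 | 14 | 42 | 56 | 28 |
| 7+ | 28 | 84 | 112 | 42 |

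Only the weekly case fits its stated delay.

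**3. How far apart the stop rules are.** Count missed doses by the Table 21 windows. The m-th consecutive dose is then missed once the hold exceeds (m − 1) × interval + window, with windows of 3, 7 and 14 days.

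| Cycles | Third dose missed from day | Fourth dose missed from day |
|---|---|---|
| 1–2 | 2×7+3+1 = 18 | 3×7+3+1 = 25 |
| 3–6 | 2×14+7+1 = 36 | 3×14+7+1 = 50 |
| 7+ | 2×28+14+1 = 71 | 3×28+14+1 = 99 |

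For a drug-related event, 6.4.1.5 stops at the earlier of the third missed dose and day 29. That is day 18, 29 and 29 for the three periods. The dose count in 10.1.1 is reached on day 25, 50 and 99. For an event unrelated to daratumumab, 6.4.1.5 stops on day 18, 36 or 71, and the 10.1.1 bullet does not apply. If the delay wording in 10.1.1 is instead read as a separate limit, the Cycle 7+ comparison is 28 days against 42.

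**The case against.** **The late-dose texts can both be met.** A reader might infer that the two texts cannot be followed together at all. That goes too far. A site that doses on day +28 and records a delayed Day 1 stays within the 4-week allowance and uses Table 21's restart date. Section 6.4.1.5 is also permissive: dosing may resume at the next planned date, and delays can be discussed with the Sponsor. This narrows the conflict to recovery on days 15 to 27, where it remains. The Sponsor option does not say which text governs. In Cycles 1 to 6 the rows can be read as covering Days 8, 15 and 22 only; Cycle 7+ has no such days.

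**The stop rules can both be met.** One section says when treatment should stop and the other when it must. A stricter rule beside a mandatory outer limit is workable, and a site that follows 6.4.1.5 complies with both. The other six bullets of 10.1.1, including investigator safety judgment and unacceptable toxicity, still operate. All of this stands. It does not repair the bullet's mismatch between dose count and delay.

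**Reachability.** A reader might infer that the 10.1.1 bullet can never be triggered, because a run of missed doses ends at every Day 1. The documents do not support that, since it presumes that the never-skip rule wins the conflict that 6.4.1.5 leaves open. Counted by Table 21 windows, the fourth missed dose in weekly dosing falls on day 25, inside the 28-day delay.

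**Impact.** Enrollment is closed, eCRF entry stops once Amendment 2 is implemented at a site (17.5), and the analysis is descriptive (11.12). This limits the consequence to conduct.

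**Conclusion.** The point holds in two limited parts.

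- For a Cycle 7+ dose with recovery 15 to 27 days late, 6.4.1.5 supports two dosing dates, 1 to 13 days apart.
- The missed-dose bullet of 10.1.1 is looser than 6.4.1.5 in dose count, adverse-event scope and Cycle 7+ delay. Its count does not fit its own delay in Cycles 3 to 6 (at least 42 days against 28) or in Cycle 7+ (at least 84 against 42).

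The interval figures rest on the protocol's schedule and the assumptions listed with the calculation. The documents do not give the number of ongoing subjects, so the number affected is unknown. No sample size, analysis or reported statistic changes. The correction is worth making because it is cheap and these rules govern dosing during toxicity.

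**What to change.** (a) In 6.4.1.5, state that Table 21 applies to within-cycle doses (Days 8, 15 and 22) and remove its Cycle 7+ row. State that a late Day 1 dose is given on recovery, up to 28 days late, with later cycles shifted as 6.4 says. The documents do not show which instruction the Sponsor intended, so the Sponsor should confirm this choice. In its favour, the row repeats Table 7 of 6.1.5, which has no Day 1 rule, while the Day 1 rule was written for this period.

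(b) Replace the missed-dose bullet in 10.1.1 with a reference to the 6.4.1.5 stop rule. Keep that rule unchanged for all cycles: a hold of more than 28 days for a drug-related event, or three or more consecutive missed doses for any adverse event. Limiting the three-dose stop to early cycles would loosen a safety stop that 6.4.1.5 does not limit.

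(c) Optionally, require Sponsor consultation for a Cycle 7+ Day 1 delay of more than 14 days. Once Day 1 is never skipped, the existing trigger of two consecutive missed doses would not fire there.

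The cost is a protocol clarification or short amendment to 6.4.1.5, Table 21 and one bullet of 10.1.1. Data collection and analysis are unaffected.
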